## 9 CLINICAL MONITORING

Clinical site monitoring is conducted to ensure that the rights and well-being of subjects are protected, that the reported trial data are accurate, complete, and verifiable from source documents, and that the trial is being conducted in compliance with the currently approved protocol/amendment(s), with GCP, and with applicable regulatory requirements.

Case report forms and other related study documentation will be reviewed as MED-EL receives the completed paperwork throughout the duration of the study. Completed study records will be reviewed 100% for missing data entries. Accuracy of study records will be monitored based on the investigator's history, accuracy of study records, the rate of occurrence of known risks, and the occurrence of protocol deviations.

## 10 STATISTICAL CONSIDERATIONS

## 10.1 STATISTICAL HYPOTHESES

The primary endpoint is change in the AzBio sentence score from pre-operative levels to 3 months. An increase of 10 percentage points in this score is considered clinically relevant. The hypotheses to be tested are:

Ho: μΔ < 10 Ha: μΔ ≥ 10

where  $\mu\Delta$  is the mean change in the AzBio sentence scores from pre-operative to 3 months post-operative. These scores are represented as a percentage of words accurately repeated during testing.

## 10.2 DESCRIPTION OF STATISTICAL METHODS

## 10.2.1 GENERAL APPROACH

Continuous variables will be summarized using mean, median, inter-quartile range, minimum, and maximum values. Categorical variables will be summarized using counts and percents. Testing of the primary endpoint will be done at the 0.025 level of significance.

## 10.2.2 ANALYSIS OF THE PRIMARY ENDPOINTS

The mean change in AzBio sentence score from baseline to 3 months post-activation will be summarized as a continuous variable using the descriptive statistics described in section 10.4.1. Additionally, a one-sided, paired t-test comparing the mean change in AzBio sentence score to the superiority margin of 10 will be performed and the corresponding p-value will be reported. A p-value less than 0.025 will result in rejection of the null hypothesis indicating that the mean change in AzBio sentence score was greater than 10 percentage points.

The rate of occurrence of known risks will be summarized and reported as the number and proportion of subjects experiencing an event.

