## STATEMENT OF COMPLIANCE

The trial will be carried out in accordance with Good Clinical Practice (GCP), as required by the following:

- United States Code of Federal Regulations (CFR) applicable to clinical studies (21 CFR Part 50, 21 CFR Part 54, 21 CFR Part 56)
- Good Clinical Practices

All investigators involved in the conduct of this study will be informed about their obligations in meeting the above commitments.

PROTOCOL SUMMAR	Υ
Title:	Outcomes in Adults with Mixed or Conductive Hearing Loss Implanted
	with the BONEBRIDGE
Study Description:	Approximately thirty subjects with mixed or conductive hearing loss,
	meeting FDA-cleared candidacy criteria for the BONEBRIDGE, will be
	implanted and followed for three (3) months post-activation to assess
	safety and effectiveness of the BONEBRIDGE implant.
Objectives:	Primary: To assess safety and effectiveness of the BONEBRIDGE
	implant in adults with mixed or conductive hearing loss.
	Secondary: To assess post-operative audiometric and speech
	perception outcomes with BONEBRIDGE, compared to unaided pre-
	operative performance as well as report on intraoperative experience.
Endpoints:	1. Subjects will demonstrate significant improvement in AzBio
(Primary)	Sentence score in noise in the implanted ear at three (3) months post-
	activation, compared to unaided pre-operative performance.
	2. Safety data will be collected and reported as the number and
	proportion of subjects experiencing known risks of the BONEBRIDGE
(Cocondon)	implant through three (3) months post-activation.
(Secondary)	1. Subjects will demonstrate similar or better scores on CNC words in
	quiet in the implanted ear at three (3) months post-activation, compared to unaided pre-operative performance.
	2. Subjects will demonstrate similar or better soundfield thresholds in
	the implanted ear at three (3) months post-activation, compared to
	pre-operative unaided soundfield thresholds.
	3. Subjects will demonstrate similar or better performance on the
	QuickSIN in the implanted ear at three (3) months post-activation,
	compared to unaided pre-operative performance.
	4. Subjects will demonstrate stable bone conduction thresholds at the
	device activation interval compared to pre-operative bone conduction
	thresholds.
Study Population:	Approximately thirty (30) total subjects, 18 years of age and older, will
, .p.	be implanted across three study sites in the United States and Canada.

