## 4.2 STUDY ENDPOINTS

## 4.2.1 PRIMARY ENDPOINTS

Primary endpoints are as follows:

- 1. Comparison of AzBio sentence score in noise with the BONEBRIDGE at three months post-activation to the pre-operative unaided score. Testing will be completed in the soundfield at 60 dB SPL with a +5 dB signal-to-noise ratio (SNR). Improvement will be defined as equal to or greater than 10 percentage points.
- 2. Number and proportion of subjects experiencing known risks, as listed above in Section 2.2.1.

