## 5 STUDY ENROLLMENT AND WITHDRAWAL

## 5.1 PARTICIPANT INCLUSION CRITERIA

Individuals must meet all of the inclusion criteria set forth below in order to qualify for inclusion in this study.

- Adults, 18 years of age or older at the time of implantation
- Conductive or mixed hearing loss, defined as:
  - Conductive hearing loss with pure-tone average (PTA) for bone conduction thresholds better than or equal to 25 dB at 500, 1000, 2000 and 3000 Hz
  - Mixed hearing loss with PTA for bone conduction thresholds better than or equal to 45 dB at 500, 1000, 2000, and 3000 Hz
- Sufficient air-bone gap at 500, 1000, 2000, and 3000 Hz to demonstrate potential for improvement
- Ability to benefit from amplification as defined by an unaided word recognition score of 30% correct or better
- Bilateral BONEBRIDGE can be considered if the difference in PTA for bone conduction thresholds is 10 dB or less between the right and left ears
- Prior experience with acoustic or bone conduction hearing aids, unless candidate is unable to wear amplification for medical reasons
- Able to complete testing materials in English
- CT scan indicating the patient's anatomy is adequate to enable placement of the implant
- Ability to undergo general anesthesia
- Appropriate motivation and expectation levels
- Stated willingness to comply with all study procedures for the duration of the study

[figure not shown]

FIGURE 1 – Example inclusion audiogram showing audiometric threshold criteria.

NOTE: Subjects may fall outside of the shaded area but still meet the PTA criteria.

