## 7.2 STUDY SCHEDULE

## 7.2.1 ENROLLMENT/BASELINE

Prior to completing any candidacy or baseline testing, subjects will sign an informed consent (IC) form.

All testing should occur in a sound-treated booth under insert earphones or in the soundfield with the subject seated one meter from the speaker, depending on the test condition. Speaker output should be calibrated prior to conducting study-related testing to ensure consistency

across clinical trial sites. During soundfield measures, the contralateral ear should be plugged or masked, as needed, taking special consideration for unilateral conductive or mixed hearing losses.

If a subject qualifies for bilateral BONEBRIDGE implantation, each ear will be treated separately.

Baseline testing will include the following outcome measures:

- Unaided audiogram, insert earphones (if patent ear canal)
  - Pure-tone air conduction thresholds (250 8000 Hz)
  - Pure-tone bone conduction thresholds (500 4000 Hz)
- Unaided speech testing in noise, soundfield
  - AzBio Sentences in noise at 60 dB SPL with an SNR of +5 dB
  - Speech and noise will be presented at 0° azimuth
  - o One list of 20 sentences will be presented to the individual implant ear(s) alone
  - Lists will be randomized at each clinical trial site
  - o Contralateral ear plugged or masked, as needed
- Unaided speech testing in quiet, soundfield
  - CNC Words in quiet at 60 dB SPL
  - o One list of 50 words will be presented to the individual implant ear(s) alone
  - o Lists will be randomized at each clinical trial site
  - o Contralateral ear plugged or masked, as needed
- Unaided audiogram, soundfield
  - o Soundfield thresholds (500 4000 Hz) in the individual implant ear(s) alone
  - Contralateral ear plugged or masked, as needed
- Unaided signal-to-noise ratio testing, soundfield
  - QuickSIN at 60 dB SPL in the individual implant ear(s) alone
  - Speech and noise will be presented at 0° azimuth
  - Lists will be randomized at each clinical trial site
  - Reported as a signal-to-noise ratio loss
  - o Contralateral ear plugged or masked, as needed
- Subjective questionnaires
  - SSQ12 & HDSS

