## 7.2.6 THREE MONTHS POST-ACTIVATION

The three-month follow-up visit will occur 10 to 14 weeks post-activation. All audiometric testing should occur in a sound-treated booth in the sound field, with the subject seated one meter from the speaker. Speaker output should be calibrated prior to conducting study-related testing to ensure consistency across study sites. During soundfield measures, the contralateral ear should be plugged or masked as needed, taking special consideration for unilateral conductive or mixed hearing losses. In the case of bilateral implantation, each ear should be tested separately.

Testing should occur with the SAMBA Audio Processor and be completed prior to making programming changes to the subject's processor. Testing should be conducted using the patient's preferred program and volume settings. The following testing should be completed:

- Aided speech testing in noise, soundfield
  - AzBio Sentences in noise at 60 dB SPL with an SNR of +5 dB
  - Speech and noise will be presented at 0° azimuth
  - One list of 20 sentences will be presented to the individual implant ear(s) alone
  - Lists will be randomized at each clinical trial site
  - Contralateral ear plugged or masked, as needed
- Aided speech testing in quiet, soundfield
  - CNC Words in quiet at 60 dB SPL
  - One list of 50 words will be presented to the individual implant ear(s) alone

- o Lists will be randomized at each clinical trial site
- o Contralateral ear plugged or masked, as needed
- Aided audiogram, soundfield
  - o Soundfield thresholds (500 4000 Hz) in the individual implant ear(s) alone
  - o Contralateral ear plugged or masked, as needed
- Aided signal-to-noise ratio testing, soundfield
  - o QuickSIN at 60 dB SPL in the individual implant ear(s) alone
  - o Speech and noise will be presented at 0° azimuth
  - o Lists will be randomized at each clinical trial site
  - o Reported as a signal-to-noise ratio loss
  - o Contralateral ear plugged or masked, as needed
- Subjective questionnaires
  - o SSQ12 & HDSS

Programming should be completed according to the IFU for SYMFIT software.

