## 10.4 SITE POOLABILITY

Poolability of the data collected at the three centers will be established in the following manner. For each subject, the change from baseline to 3 months in the AzBio sentenc score will be

computed. The changes in AzBio sentence score will be analyized using a one-way analysis of variance in which site forms the levels of the single factor. The overall F-test will be used to demonstrate poolability of the primary endpoint data. If the p-value for the overall F-test is greater than or equal to 0.10 then the data will be considered poolable. If the p-value is less than 0.10, then additional methods (e.g. stratified analysis) may need to be employed in the analysis of the primary endpoint.

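### Does the plan need a written rule for how a bilateral subject's two AzBio changes enter the primary t-test?

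*Combined protocol and SAP*

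**What the plan says.** The analysis sections speak of a single AzBio change. Section 10.2.2 states that "a one-sided, paired t-test comparing the mean change in AzBio sentence score to the superiority margin of 10 will be performed". Section 10.3 counts 30 subjects, and Section 10.4 works with "For each subject, the change from baseline to 3 months in the AzBio sentenc score". The Protocol Summary places the primary endpoint in one ear ("Sentence score in noise in the implanted ear"). Section 4.2.1 names no ear: "Comparison of AzBio sentence score in noise with the BONEBRIDGE at three months post-activation to the pre-operative unaided score".

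The eligibility and testing sections allow two ears. Section 5.1 says "Bilateral BONEBRIDGE can be considered if the difference in PTA for bone conduction thresholds is 10 dB or less between the right and left ears", with no cap and no expected number. Section 7.2.1 says of the AzBio test that "One list of 20 sentences will be presented to the individual implant ear(s) alone", and 7.2.5 and 7.2.6 repeat this at one and three months. On bilateral cases, 7.2.1 adds "If a subject qualifies for bilateral BONEBRIDGE implantation, each ear will be treated separately" and 7.2.6 adds "In the case of bilateral implantation, each ear should be tested separately".

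Neither 10.2.2, 10.2.4 nor 10.4 gives a rule for combining or selecting ears.

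**The concern.** A bilateral subject has two AzBio changes and the test appears to need one. The mean of the ears, the right ear, the left ear and the better ear are all one value per subject, so the plan's wording does not fix a single p-value for its only formal test. The study is single-arm and no blinding is described, so whoever runs the test could see both ears' scores before choosing. Section 4.2.2 refers to the individual implant ear(s) and a same-ear comparison for the secondary endpoints, which makes the silence in 4.2.1 and 10.2.2 more noticeable. If the choice could raise the false-success rate above 2.5%, or often reverse the verdict, the plan would need a written rule.

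**Working it through.** **Inputs from the documents.** n = 30, mean change 30, SD 30 (10.3); margin 10 and one-sided alpha 0.025 (10.2.2).

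**Assumptions not in the documents.** k bilateral subjects out of 30; between-ear correlation of changes from 0.9 down to 0.3; normal changes with SD 30 in each ear.

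**Step 1: the plan's own figure.** Standard error = 30/√30 = 5.48. Noncentrality = (30 − 10)/5.48 = 3.65. The noncentral t with 29 degrees of freedom gives power 94.16%, which matches the stated 94.2% for one value per subject.

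**Step 2: where the verdict turns.** The observed mean needed is 10 + 2.045 × 5.48 = 21.2. The planned mean of 30 lies 30 − 21.2 = 8.8 points above it.

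**Step 3: how far an ear rule can move the mean.** If k subjects have ears differing by g points, moving from the mean of ears to all better or all worse ears shifts the overall mean by k × g/(2 × 30). For k = 3 and g = 10 this is 0.5 points. The verdict can flip only close to 21.2: in constructed data with SD about 30, the worse ear gives a mean of 21.0 (p = 0.027), the mean of ears 21.5 (p = 0.022) and the better ear 22.0 (p = 0.0185).

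**Step 4: how often ordinary rules disagree.** 400,000 simulated trials per cell; chance that mean, right-ear and left-ear values do not all give the same verdict (correlation 0.9 to 0.3):

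| Bilateral subjects | True change 30 (planned) | True change 20 |
|---|---|---|
| 0 | 0 | 0 |
| 1 | 0.7–1.9% | 2.4–6.5% |
| 3 | 1.3–3.4% | 4.5–11.9% |
| 6 | 1.9–4.8% | 6.5–17.2% |
| 10 | 2.5–6.3% | 8.3–22.7% |

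The right-hand column is not a planning scenario. A true mean of 20 is below the 21.2 needed, and power there is only about 42%.

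**Step 5: error at true change 10 (nominal 2.5%).**

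| Rule | k = 1 | k = 3 | k = 10 |
|---|---|---|---|
| Mean of ears, or an ear fixed in advance | 2.4–2.6% | 2.4–2.6% | 2.4–2.6% |
| Most favourable of mean/right/left, chosen after seeing data | 2.7–3.0% | 2.9–3.4% | 3.1–4.1% |
| Better ear | 2.7–3.0% | 3.2–4.3% | 4.9–12.7% |

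The first row is nominal within simulation error. Entering both ears as if independent gives about 2.6–2.8% with one bilateral subject and 2.8–3.5% with three.

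**Step 6: power under an ordinary rule.** A separate run (20,000 trials per cell, correlations 0.5 and 0.7, 3 to 10 bilateral subjects) gave about 94% for a fixed ear and 94.6–95.8% for the mean of ears. The stated power is met either way.

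**The case for a change.** The strongest case for acting is that this is the only formal test, the scores are open, and a sentence would cost almost nothing. The planning values come from a trial of a different system, so a true change nearer the margin cannot be excluded, and ordinary rules would then disagree more often. The per-subject wording in 10.3 and 10.4 does not settle the matter: those sections cover sample size and site pooling, so the unit for the t-test is implied rather than stated. The instruction in 7.2.1 to treat ears separately could even be read as pointing to ear-level analysis.

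Most of this stands as description. The unit is indeed only implied. But the 7.2.1 sentence sits among test instructions, and reading it as an analysis rule would conflict with 10.3 and 10.4. Disagreement between two valid rules is also not an error, since each holds 2.5% alone. The larger error rates belong to rules that no text in Section 10 states. Even deliberate selection among mean, right and left reaches only 2.9–3.4% with three bilateral subjects.

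A related argument is that ears with bone-conduction averages of 20 and 30 dB, which 5.1 allows in a bilateral subject, leave that subject without a single hearing loss type for 10.2.6. This does not follow. Both ears meet the 45 dB mixed limit as written, because 5.1 sets no lower bound for mixed loss. The ears may be classified differently because the two limits overlap, but that overlap applies to unilateral subjects too, and 10.2.6 is descriptive.

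**Conclusion.** The plan leaves unstated how two ear-level AzBio changes become one value, but no change is called for. Any rule that does not depend on the outcome keeps the error at 2.5% and at least the stated power, and an analyst following 10.3 and 10.4 would ordinarily take the mean of the ears or a fixed ear. At the planning values, the choice among mean, right and left ear matters in about 1.3–3.4% of trials with three bilateral subjects, and in none without bilateral subjects. These sizes rest on an assumed number of bilateral subjects, a between-ear correlation of 0.3 to 0.9, and normal changes with SD 30. The judgement would be different if many subjects were bilateral and a better-ear or after-the-fact choice were actually used, and the documents give no sign of either.

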## 10.2.3 ANALYSIS OF THE SECONDARY ENDPOINT(S)

Secondary endpoints will not be formally tested but will be summarized using appropriate descriptive statistics.

The number and percentage of subjects performing similarly or better on CNC words, soundfield thresholds, QuickSIN, and bone conduction thresholds at 3 months post-activation, compared to the pre-operative unaided condition, will be presented. The formal definitions of what is considered worse, similar, and better are presented in section 4.2.2.

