## 4.2.2 SECONDARY ENDPOINTS

Secondary endpoints are as follows:

- CNC word score in quiet with the BONEBRIDGE at three months post-activation in the
  individual implant ear(s), compared to the pre-operative unaided score in the same ear.
  Testing will be completed in the soundfield at 60 dB SPL. Scores at three months will be
  similar to or better than scores at the pre-operative interval. Similar is defined as within
  10 percentage points, while better than is defined as equal to or greater than a 10percentage-point change. Subjects will be classified as improved, similar, or worse at
  three months post-activation.
- 2. Soundfield thresholds with the BONEBRIDGE at three months post-activation in the individual implant ear(s) at 500-4000 Hz, compared to pre-operative soundfield thresholds in the same ear. Thresholds at three months will be similar to or better than scores at the pre-operative interval. Similar is defined as thresholds within 15 dB at five or more of the frequencies tested, while better is defined as a 15 dB improvement in thresholds at three or more frequencies tested. Subjects will be classified as improved, similar, or worse at three months post-activation.
- 3. QuickSIN score with the BONEBRIDGE at three months post-activation in the individual implant ear(s), compared to the pre-operative unaided score in the same ear. Scores at three months will be similar to or better than scores at the pre-operative interval. Similar is defined as within 1 dB SNR, while better than is defined as equal to or greater than than a 1 dB SNR decrease. Subjects will be classified as improved, similar, or worse at three months post-activation.
- 4. Bone conduction thresholds from the device activation interval will be compared to the pre-operative interval to assess stability in the implant ear(s). A worsening in bone conduction thresholds is defined as a 15 dB or greater decrease. Bone conduction thresholds will be considered stable if no more than two frequencies demonstrate a worsening.

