## 7.2.3 DEVICE ACTIVATION

Device activation will occur two to four weeks after surgery. Prior to fitting the device, the following testing should be completed:

- Unaided audiogram, insert earphones (if patent ear canal)
  - o Pure-tone air conduction thresholds (250 8000 Hz)
  - o Pure-tone bone conduction thresholds (500 4000 Hz)

Investigators should fit the SAMBA Audio Processor in accordance with the instructions in the IFU for SYMFIT software.

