# 7.2.7 SCHEDULE OF EVENTS TABLE

		Candidacy/ Pre-op	Surgery	Activation	2 weeks post- activation	1 month post- activation	3 months post- activation
	Informed Consent	X					
	Medical Assessment	Х					
	Surgery	V	Χ	V			
	Unaided thresholds	Х		Χ			
Implant Ear(s)	AzBio 60 dB SPL +5 dB SNR	Unaided				Aided	Aided
Implant ear(s)	CNC Words 60 dB SPL quiet	Unaided				Aided	Aided
Implant ear(s)	Soundfield thresholds	Unaided			Aided		Aided
Implant ear(s)	QuickSIN 60 dB SPL	Unaided				Aided	Aided
	SSQ12	Χ					Χ
	HDSS	Χ					Χ

(TABLE 1)

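### Bone-conduction stability endpoint: Section 10.2.3 names a visit without the test, Section 10.2.6 names a measure no visit collects, and Section 4.2.2 words the direction of worsening the wrong way round

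*Combined protocol and SAP*

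**What the plan says.** The same endpoint, or a summary linked to it, appears in several places.

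- **Protocol Summary, secondary endpoint 4:** "Subjects will demonstrate stable bone conduction thresholds at the" device activation interval, relative to pre-operative thresholds.
- **Section 4.2.2, item 4, visit:** "Bone conduction thresholds from the device activation interval will be compared to the pre-operative interval to assess stability in the implant ear(s".
- **Section 4.2.2, item 4, rule:** "A worsening in bone conduction thresholds is defined as a 15 dB or greater decrease". An ear is "considered stable if no more than two frequencies demonstrate a worsening".
- **Section 7.2.3:** air- and bone-conduction thresholds are measured unaided at activation, before the processor is fitted.
- **Section 7.2.6:** the only threshold test at three months is headed "Aided audiogram, soundfield". No bone-conduction test is listed.
- **Table 1 (Section 7.2.7):** the row "Unaided thresholds" is marked at the pre-operative visit and at activation only.
- **Section 10.2.3:** the analysis text groups bone conduction with three other endpoints: "soundfield thresholds, QuickSIN, and bone conduction thresholds at 3 months post-activation, compared to the pre-operative unaided condition, will be presented". It refers to Section 4.2.2 for the definitions of worse, similar and better.
- **Section 10.2.6:** change in AzBio score and change in *aided* bone-conduction thresholds are to be summarised by type of hearing loss.

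**The concern.** Three statements do not fit the rest of the document.

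1. **Visit.** Section 10.2.3 places the bone-conduction result at a visit where bone conduction is not measured.
2. **Measure.** Section 10.2.6 names a measure that is not collected. It could mean unaided bone conduction or aided soundfield thresholds, and these answer different questions: whether the inner ear was preserved, or how much the device helps.
3. **Direction.** Item 4 calls a decrease in threshold a worsening, which is the opposite of how the protocol uses the dB scale elsewhere.

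Safety is part of the primary objective, and hearing loss is not named in either list of known risks (Sections 2.2.1 and 8.1.1). Item 4 is therefore the only pre-specified numeric criterion for loss of bone-conduction hearing after surgery. Sections 8.1.2 and 8.2 would still allow related hearing loss to be reported as an event, but without a threshold. If the three statements stay as they are, the analyst has to reconcile them, possibly after seeing the data in a single-arm study. A table labelled three months would also overstate how long stability had been observed.

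**Working it through.** The plan gives no numerical figure for this endpoint. Its one design figure, 94.2% power for the AzBio test, reproduces at 94.16% (noncentral t, n = 30, difference 30 − 10 = 20, SD 30, one-sided 0.025). It plays no part in this point.

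**Visit.** The visit lists and Table 1, side by side:

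| Visit | Bone conduction listed? | Other tests relevant here |
|---|---|---|
| Pre-operative (7.2.1) | Yes, unaided | Unaided soundfield thresholds |
| Activation (7.2.3) | Yes, unaided, before fitting | Air conduction |
| 2 weeks (7.2.4) | No | Aided soundfield thresholds |
| 1 month (7.2.5) | No | Aided speech tests |
| 3 months (7.2.6) | No | Aided soundfield thresholds and speech tests |

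Bone conduction is thus scheduled at 1 of 4 post-operative test visits and at 0 of the 3 post-activation visits. Section 7.1.1 speaks of pre- and post-operative testing for air conduction, but names no 3-month bone-conduction test.

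Timing, from the windows in Section 7.1.2:

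- Activation: 2 to 4 weeks after surgery.
- Three-month visit: 10 to 14 weeks after activation.
- Three-month visit counted from surgery: 2 + 10 = 12 weeks to 4 + 14 = 18 weeks.

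**Measure.** In the table, every bone-conduction test is unaided, and every aided threshold is a soundfield threshold. No cell is both aided and bone conduction. Only that part of the Section 10.2.6 summary is undefined; the AzBio part is not affected.

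**Direction.** Sections 1 and 5.1 treat lower dB as better, for example in requiring a pure-tone average better than or equal to 25 dB or 45 dB. Item 3 of Section 4.2.2 also uses *decrease* for a numerical fall, and there it means improvement.

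Let d be the threshold at activation minus the pre-operative threshold, at each of the five frequencies in Section 7.1.1 (500, 1000, 2000, 3000 and 4000 Hz).

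- Literal rule: a frequency is worse if d ≤ −15.
- Intended rule: a frequency is worse if d ≥ +15.
- Under both, the ear is stable if at most two frequencies are worse.

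If at least three frequencies have d ≥ +15, at most 5 − 3 = 2 can have d ≤ −15, so the literal rule always returns stable. Two test cases:

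| Change at all five frequencies | Literal rule | Intended rule |
|---|---|---|
| 20 dB poorer (d = +20) | Stable | Not stable |
| 20 dB better (d = −20) | Not stable | Stable |

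The two rules disagree only for ears in which three or more frequencies shift by 15 dB or more in the same direction.

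**Size of the direction effect.** Assume 30 subjects, one ear each, with both measurements. Each misclassified subject moves the percentage by 1/30 = 3.3 points. The documents give no expected number of such subjects, so the range is shown, assuming that no ear improves by that much:

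| Subjects truly not stable (assumed) | Percentage stable, intended | Percentage stable, literal |
|---|---|---|
| 0 | 30/30 = 100 | 100 |
| 1 | 29/30 = 96.7 | 100 |
| 2 | 28/30 = 93.3 | 100 |
| 3 | 27/30 = 90.0 | 100 |

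**The case against.** The best case against is that these are drafting slips, and that the document itself resolves two of them.

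- **Visit.** Only activation data will exist, and Section 10.2.3 sends the reader to Section 4.2.2, which names activation. The sentence probably attached to four endpoints a time point that is right for three. This stands: the choice of visit is nearly forced. But the analysis text still states a result that cannot be produced, and the contradiction remains until the text is changed.
- **Direction.** The sentence defines a worsening, so a reader who programs it backwards has to ignore the word being defined; *decrease* may loosely mean a decrease in hearing. The intent is indeed clear. Against this, item 3 of the same list uses the word numerically, and a rule that reverses when coded as written should be corrected.
- **Size.** The percentages rest on assumed counts and on the literal reading alone. That is right, and the effect may be zero.
- **Measure.** Section 10.2.6 is a separate descriptive summary and does not use the stability rule. True, but it is the one part where the text offers no way to tell what was meant.

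Two related gaps are fairly raised. For bone conduction, Section 4.2.2 defines only worsening and stable, not the worse, similar and better categories that Section 10.2.3 relies on. And Section 10.2.3 counts subjects, while Section 7.2.1 treats the ears of bilaterally implanted subjects separately.

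**Conclusion.** The concern holds in all three parts and should be fixed before analysis. Section 10.2.3 assigns bone conduction to a visit 12 to 18 weeks after surgery, when the only post-operative test is at 2 to 4 weeks. Section 10.2.6 names a measure that is never collected. Item 4 of Section 4.2.2 classifies in reverse if coded literally.

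The consequences are limited. The endpoint is secondary, descriptive and untested; the primary test, its alpha, its power and the data collection are unaffected. The measurements needed for the endpoint as Section 4.2.2 intends it are scheduled at both relevant visits. The figure of 3.3 points per subject applies only to the literal reading, and assumes 30 subjects with one ear each and complete measurements.

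**What to change.** Make three wording corrections before analysis:

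1. **Section 10.2.3:** take bone conduction out of the 3-month list. Report the number and percentage stable versus not stable at activation, as a separate item. This also removes the reliance on categories that Section 4.2.2 does not define for bone conduction.
2. **Section 10.2.6:** have the sponsor confirm whether unaided bone-conduction change (pre-operative to activation) or aided soundfield change is meant, and name that measure.
3. **Section 4.2.2, item 4:** define worsening at a frequency as a threshold at least 15 dB higher (poorer) at activation than before surgery.

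While editing, state whether the count is by ear or by subject when both ears are implanted. The cost is editorial: no new visits, tests or subjects.
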